8.1.3. Secondary Endpoint

The secondary efficacy endpoints are

- The proportion of subjects that have HIV-1 RNA < 50 copies/mL at Week 96 as defined by the US FDA-defined snapshot algorithm.
- The change from baseline in CD4 and at Weeks 48 and 96.
- The proportion of subjects with plasma HBV DNA < 29 IU/mL at Week 96.
- The proportion of subjects with ALT normalization at Weeks 48 and 96.
- The proportion of subjects with HBsAg loss at Weeks 48 and 96

8.2. Analysis Conventions

8.2.1. Analysis Sets

8.2.1.1. All Randomized

The randomized analysis set includes all subjects who are randomized into the study. This is the primary analysis set for by-subject listings.

8.2.1.2. Efficacy

8.2.1.2.1. Full Analysis Set (FAS)

The primary analysis set for efficacy analyses is defined as full analysis set (FAS), which will include all subjects who (1) are randomized into the study, (2) have received at least 1 dose of study drug, and (3) have at least 1 post baseline HIV-1 RNA or HBV DNA results while on study drug. Subjects will be grouped according to the treatment to which they were randomized.

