6.4. Day 1 Assessments

The following evaluations are to be completed at the Day 1 Visit. **The Investigator must have received the results from the screening genotype report and confirmed eligibility before proceeding with the Day 1 visit.** The subject must complete all study procedures before being administered the study drug:

- Review of AEs and changes in concomitant medications
- Complete physical examination (urogenital/anorectal exams will be performed at the discretion of the Investigator)
- Vital signs measurement (blood pressure, pulse, respiration rate, and temperature), including weight
- Obtain blood and urine samples as described in Section 6.10
- Provide subject dosing diary to all subjects for PK collection
- Dispense study drug
- Observed first dose administration of the assigned study drugs as described in Section 5.3.
- Subjects should be instructed to take study drugs without regard to food. The subject should be counseled regarding the importance of adherence and taking their study medications at approximately the same time each day as directed by the Investigator.

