8.5. Efficacy Analysis

8.5.1. Primary Analysis

The primary efficacy endpoint is the proportion of subjects who achieve HIV-1 RNA < 50 copies/mL at Week 48 as determined by the US FDA-defined snapshot algorithm. The primary analysis of the efficacy endpoint will be based on the FAS.

The co-primary efficacy endpoint is the proportion of subjects with plasma HBV DNA < 29 IU/mL at Week 48 as determined by Missing=Failure approach. The primary analysis of this efficacy endpoint will be based on the FAS.

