8.5.1.1. The US FDA-defined Snapshot Algorithm for HIV-1

The analysis window at Week 48 is defined as from Study Day 295 to Study Day 378, inclusive. All HIV-1 RNA data collected on-treatment (ie, including data collected up to 1 day after the last dose date of study drug) will be used in the snapshot algorithm. Virologic outcome will be defined as the following categories:

- **HIV-1 RNA < 50 copies/mL:** this includes subjects who have the last available on-treatment HIV-1 RNA < 50 copies/mL in the Week 48 analysis window

- **HIV-1 RNA \geq 50 copies/mL:** this includes subjects
 - a) Who have the last available on-treatment HIV-1 RNA \geq 50 copies/mL in the Week 48 analysis window, or
 - b) Who do not have on-treatment HIV-1 RNA data in the Week 48 analysis window and
 - i) Who discontinue study drug prior to or in the Week 48 analysis window due to lack of efficacy, or
 - ii) Who discontinue study drug prior to or in the Week 48 analysis window due to reasons other than adverse event (AE), death, or lack of efficacy and have the last available on-treatment HIV-1 RNA \geq 50 copies/mL
- **No Virologic Data in the Week 48 analysis window:** this includes subjects who do not have on-treatment HIV-1 RNA data in the Week 48 analysis window because of the following:
 - a) Discontinuation of study drug prior to or in the Week 48 analysis window due to AE or death (regardless of whether the last available on-treatment HIV-1 RNA $<$ 50 copies/mL or not) or,
 - b) Discontinuation of study drug prior to or in the Week 48 analysis window due to reasons other than AE, death, or lack of efficacy and the last available on-treatment HIV-1 RNA $<$ 50 copies/mL or,
 - c) Missing data during the window but on study drug.

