8.5.1.3. Analysis of Co-Primary Efficacy Endpoint for HBV

The null hypothesis is that the proportion of subjects with plasma HBV DNA < 29 IU/mL at Week 48 as determined by Missing=Failure approach in B/F/TAF is at least 12% lower than the response rate in DTG + F/TDF; the alternative hypothesis is that the response rate in B/F/TAF is less than 12% lower than that in DTG + F/TDF. For Missing = Failure approach, all missing data will be treated as HBV DNA \geq 29 IU/mL.

Non-inferiority will be assessed similarly as for the primary efficacy endpoint, except the stratification factors include HBeAg status (positive vs. negative) and baseline HBV DNA (< 8 log₁₀ IU/mL vs. \geq 8 log₁₀ IU/mL). To control type I error for the assessment of the primary and the co-primary efficacy endpoints, the hypothesis testing will be performed using the fallback procedure {[Wiens 2005](#)} in the sequential order with pre-specified 1-sided alpha level. The primary hypothesis of non-inferiority of B/F/TAF relative to DTG + F/TDF, with respect to the proportion of subjects with HIV-1 RNA < 50 copies/mL at Week 48 (as defined by the FDA snapshot analysis) will be tested first. Non-inferiority test will be performed at one-sided, 0.025 alpha level. If non-inferiority is established, the co-primary hypothesis of non-inferiority of B/F/TAF relative to DTG + F/TDF, with respect to the proportion of subjects with plasma HBV DNA < 29 IU/mL at Week 48 will be tested second at one-sided, 0.025 alpha level. Otherwise, the co-primary endpoint will not be tested at all.

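### The FAS used for both Week 48 non-inferiority tests drops dosed subjects who stop before any on-drug viral load, although none of them could be an HIV snapshot success

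*Protocol*

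**What the plan says.** Protocol Section 8.2.1.2.1 sets three conditions for the FAS: randomization, at least one dose, and the requirement to "have at least 1 post baseline HIV-1 RNA or HBV DNA results while on study drug". Either assay is enough. Section 8.5.1 applies this set to the HIV endpoint ("The primary analysis of the efficacy endpoint will be based on the FAS") and to the HBV endpoint ("The primary analysis of this efficacy endpoint will be based on the FAS").

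Four other provisions decide who is lost:

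- Section 6.4: "The subject must complete all study procedures before being administered the study drug". Day 1 samples therefore precede dosing and do not count as post-baseline.
- Section 6.5: the first scheduled sample after Day 1 is at Week 4.
- Section 6.8.1: the early-discontinuation visit may take place up to 72 hours after stopping.
- SAP Appendix 7, item 8: for the FAS, being on study drug ends 1 day after permanent discontinuation.

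On outcomes, Section 8.5.1.1 limits HIV success to "subjects who have the last available on-treatment HIV-1 RNA < 50 copies/mL in the Week 48 analysis window". Section 8.5.1.3 treats all missing HBV DNA as not below 29 IU/mL ("For Missing = Failure approach, all missing data will be treated as HBV DNA" at or above that limit). If HIV non-inferiority fails, "Otherwise, the co-primary endpoint will not be tested at all".

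**The concern.** Membership of the set used for both primary tests depends on something that happens after randomization. A subject who takes a few doses, stops for intolerance or withdraws, and has no sample within a day of the last dose disappears from numerator and denominator. The snapshot and Missing = Failure rules exist to count subjects without Week 48 data as non-responders, and the FAS condition removes some of them before those rules apply.

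The effect depends on imbalance. More exclusions on B/F/TAF raise its response rate and favour non-inferiority; more on control work against it. Because HBV is tested only after HIV passes, a changed HIV conclusion also decides whether HBV is tested.

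The documents supplied contain no all-treated efficacy analysis. The per-protocol sets (Sections 8.2.1.2.2 and 8.2.1.2.3) are narrower, and SAP Section 6.4 plans no change from the protocol's efficacy analysis.

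**Working it through.** **Inputs.** Protocol Section 8.8 gives 120 per arm, a margin of 12 points, one-sided alpha of 0.025, and response in both arms of 91% (HIV) and 88% (HBV). SAP Appendix 3 gives 243 in the Safety Analysis Set. The FAS count is not given, so the early-loss rates below are assumptions.

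**Plan's own power.** Power = Φ(0.12/SE − 1.96), with SE = √(2p(1−p)/120).

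- HIV: SE = √(2 × 0.91 × 0.09/120) = 0.0369; 0.12/0.0369 = 3.25; Φ(1.29) = 0.901, against 90% stated.
- HBV: SE = √(2 × 0.88 × 0.12/120) = 0.0420; 0.12/0.0420 = 2.86; Φ(0.90) = 0.816, against 81% stated.

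Both reproduce.

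**Outcome of an excluded subject.** HIV success needs an on-treatment value in the Week 48 window. An excluded subject has no on-treatment value, so the chance of success is exactly zero. Section 8.5.1.1 gives a non-success category to stops for AE, death or lack of efficacy. For stops "due to reasons other than AE, death, or lack of efficacy and the last available on-treatment HIV-1 RNA" must be known under both available routes, so a subject with none has no literal category. For HBV, an excluded subject with no Week 48 value would be a failure. Whether off-drug HBV DNA counts at Week 48 is a separate question; the HBV figures below assume failure.

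**Error rates and power.** Exact enumeration with 120 treated per arm. Successes X ~ Bin(120, s). Early losses given X ~ Bin(120 − X, l/(1 − s)), where l is the early-loss rate. The FAS removes the losses from the denominator. Non-inferiority is declared if the unstratified Wald 95% lower bound exceeds −12%. Type I error is taken at a true all-treated difference of −12 points (79% vs 91% for HIV, 76% vs 88% for HBV); power is at equal efficacy.

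| Early loss, B/F/TAF / control | HIV type I error | HBV type I error | HIV power | HBV power |
|---|---|---|---|---|
| All treated (no exclusion) | 2.84% | 2.65% | 90.2% | 81.9% |
| FAS, 0.5% / 0.5% | 2.75% | 2.61% | 91.0% | 82.7% |
| FAS, 1% / 1% | 2.69% | 2.56% | 92.1% | 83.8% |
| FAS, 2% / 2% | 2.59% | 2.45% | 94.2% | 86.0% |
| FAS, 2% / 1% | 4.08% | 3.72% | – | – |
| FAS, 1% / 2% | 1.65% | 1.64% | 89.0% | 79.1% |

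The comparator for the FAS rows is the all-treated row, not 2.5%, because the Wald interval itself runs slightly above nominal here.

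**Single results.** Lower bound = d − 1.96 × √(p₁(1−p₁)/n₁ + p₂(1−p₂)/n₂).

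- HIV, 104/120 vs 109/120: d = −4.17, SE = 4.07 points, bound −12.1% (fails).
- HIV, 104/119 vs 109/120 (one B/F/TAF exclusion): d = −3.44, SE = 4.02, bound −11.3% (passes). With 109/120 on control and one exclusion, 104 is the only responder count that flips.
- HIV, opposite direction: 105/120 vs 109/120 gives −11.2% (passes); 105/120 vs 109/118 gives −12.5% (fails).
- HBV, control 106/120: 101/120 gives −12.9% (fails); 101/119 gives −12.1% (still fails); 101/118 gives −11.3% (passes).

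**The case against.** The strongest reply is that nothing shows an actual effect. The number excluded may be zero, either assay keeps a subject in, and a prompt discontinuation visit can rescue an early stop. The trial is blinded with matching placebos, equal loss does not inflate error, and the 4.08% needs an assumed two-to-one imbalance against B/F/TAF. All of that stands and limits the size of the point. It does not justify the exclusion, because the count by arm is not given.

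The supplied SAP covers the final analysis, and SAP Section 6.1.1 places the primary methods in a Week 48 SAP that is not available. An all-treated sensitivity analysis could be there. This stands: the claim of absence covers only the documents at hand. It also means that the on-drug definition, and the rule in SAP Section 3.1 fixing set membership before unblinding, are read back to Week 48. That rule guards against selection by known arm but not against imbalance.

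The missing snapshot category might be settled by the flowchart in SAP Appendix 2, which is not shown. It also matters mainly once the FAS condition is removed. Both are fair; the statement concerns the protocol's wording, and the fix supplies the rule.

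The HBV figures assume failure. Section 8.5.1.3 does not confine the data to on-treatment values, and subjects off drug may stay in follow-up, so those figures are conditional.

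Finally, the matching denominators in the prior study GS-US-380-1490 would also arise if the same rule excluded nobody. They are consistent with the fix but do not prove the point.

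**Conclusion.** The concern holds. Both Week 48 non-inferiority tests use a set selected after randomization, and every subject it drops is a certain HIV non-success. The direction depends on which arm loses more. Under the assumptions above, a 2% versus 1% early loss moves the HIV type I error from 2.84% to 4.08%, or to 1.65% if reversed; for HBV, 2.65% becomes 3.72% or 1.64%. Equal loss causes no inflation. A changed conclusion needs a result already close to −12%. These figures rest on 120 per arm, an unstratified Wald interval (the planned stratified Mantel-Haenszel interval will differ slightly) and assumed loss rates. No document shows unequal early loss. This should be fixed because the check is cheap and it concerns both primary tests, not because there is evidence of bias.

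**What to change.** In design terms, delete the third FAS condition so that the primary efficacy set is all randomized subjects with at least one dose, analysed as randomized. State that a subject with no on-treatment HIV-1 RNA at all is a snapshot non-responder, and that missing Week 48 HBV DNA is a failure.

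SAP Sections 2.2.1 and 2.2.2 report the Week 48 and Week 96 analyses as done, so this now becomes a sensitivity analysis beside the completed FAS result:

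1. Report the number excluded from the FAS by arm, with reasons. The disposition summary in SAP Section 4.1.2 already lists Safety Analysis Set and FAS counts, so the reasons are the addition.
2. If anyone was excluded, rerun both Week 48 tests on all treated subjects with the planned stratified Mantel-Haenszel interval, and show the two lower bounds side by side.
3. If the bounds fall on different sides of −12%, say that the conclusion depends on the exclusion. If nobody was excluded, say so; no rerun is needed.

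This would match the prior study GS-US-380-1490 in protocol Section 1.2.3.4, where the Missing = Failure denominators (320 and 325) equal the randomized and treated counts.

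The cost is one non-responder rule, a list of reasons and two reruns, with no new data. Response rates may fall slightly, and the rerun is post hoc and should be labelled so.

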8.2.1.2.2. Per-Protocol (PP) Analysis Set for anti-HIV Efficacy Analysis

The secondary analysis set for anti-HIV efficacy analyses is defined as per-protocol (PP) analysis set for anti-HIV efficacy analysis, which will include all subjects who (1) are randomized into the study, (2) have received at least 1 dose of study drug, and (3) have not committed any major protocol violation, including the violation of key entry criteria. Subjects will be grouped according to the treatment they actually received.

Subjects meeting any of the following criteria will be excluded from the Week 48 PP analysis set for anti-HIV efficacy analysis:

- Subjects who do not have on-treatment HIV-1 RNA in the Week 48 analysis window, except when missing due to discontinuation of study drug for lack of efficacy.
- Subjects who do not meet the inclusion criterion that the screening genotype report must show sensitivity to FTC and TFV.

- Subjects who meet the exclusion criterion for receiving ongoing therapy with any of the medications listed in the table in protocol Section 4.3 including drugs not to be used with bicitgravir, FTC, DTG, TAF, and TDF.
- Nonadherence to study drug: subjects with adherence rate for active study drug up to the Week 48 Visit below the 2.5th percentile

8.2.1.2.3. Per-Protocol (PP) Analysis Set for anti-HBV Efficacy Analysis

The secondary analysis set for anti-HBV efficacy analyses is defined as per-protocol (PP) analysis set for anti-HBV efficacy analysis, which will include all subjects who (1) are randomized into the study, (2) have received at least 1 dose of study drug, and (3) have not committed any major protocol violation, including the violation of key entry criteria. Subjects will be grouped according to the treatment they actually received.

Subjects meeting any of the following criteria will be excluded from the Week 48 PP analysis set for anti-HBV efficacy analysis:

- Subjects who do not have on-treatment HBV DNA in the Week 48 analysis window, except when missing due to discontinuation of study drug for lack of efficacy.
- Subjects who do not meet the inclusion criterion that the screening genotype report must show sensitivity to FTC and TFV.
- Subjects who meet the exclusion criterion for receiving ongoing therapy with any of the medications listed in the table in protocol Section 4.3 including drugs not to be used with bicitgravir, FTC, DTG, TAF, and TDF.
- Nonadherence to study drug: subjects with adherence rate for active study drug up to the Week 48 Visit below the 2.5th percentile

8.2.1.3. Safety

The primary analysis set for safety analyses is defined as safety analysis set, which will include all subjects who (1) are randomized into the study and (2) have received at least 1 dose of study drug. All the data collected up to 30 days after subjects permanently discontinue their study drug will be included in the safety summaries, unless specified otherwise. Subjects will be grouped according to the treatment they actually received.

8.3. Data Handling Conventions

HIV-1 RNA results of ‘No HIV-1 RNA detected’ and “< 20 cp/mL HIV-1 RNA Detected” will be imputed as 19 copies/mL for analysis purposes. HBV DNA results of “<20 IU/mL HBV DNA detected” or “No HBV DNA detected” will be imputed as 19 IU/mL for analysis purposes. Logarithm (base 10) transformation will be applied to HIV-1 RNA and HBV DNA data for efficacy analysis.

Laboratory data that are continuous in nature but are less than the lower limit of quantitation or above the upper limit of quantitation will be imputed to the value of the lower or upper limit plus or minus one significant digit, respectively (e.g. if the result of a continuous laboratory test is < 20 , a value of 19 will be assigned).

Missing data can have an impact upon the interpretation of the trial data. In general, values for missing data will not be imputed. However, a missing pre-treatment laboratory result would be treated as normal (i.e., no toxicity grade) for the laboratory abnormality summary.

All available data for subjects that do not complete the study will be included in data listings.

8.4. Demographic Data and Baseline Characteristics

Demographic and baseline characteristics will be summarized using standard descriptive methods including sample size, mean, SD, median, Q1, Q3, minimum, and maximum for continuous variables and frequency and percentages for categorical variables.

Demographic data will include sex, race, ethnicity, and age.

Baseline characteristics will include body weight, height, body mass index, eGFR, HIV-1 infection, HBV infection, and enrollment distribution by randomization stratum will be summarized.

For categorical demographic and baseline characteristics, the Cochran–Mantel–Haenszel (CMH) test will be used to compare treatment groups. For continuous demographic and baseline characteristics, the Wilcoxon rank sum test will be used to compare treatment groups.

8.5. Efficacy Analysis

8.5.1. Primary Analysis

The primary efficacy endpoint is the proportion of subjects who achieve HIV-1 RNA < 50 copies/mL at Week 48 as determined by the US FDA-defined snapshot algorithm. The primary analysis of the efficacy endpoint will be based on the FAS.

The co-primary efficacy endpoint is the proportion of subjects with plasma HBV DNA < 29 IU/mL at Week 48 as determined by Missing=Failure approach. The primary analysis of this efficacy endpoint will be based on the FAS.

8.5.1.1. The US FDA-defined Snapshot Algorithm for HIV-1

The analysis window at Week 48 is defined as from Study Day 295 to Study Day 378, inclusive. All HIV-1 RNA data collected on-treatment (ie, including data collected up to 1 day after the last dose date of study drug) will be used in the snapshot algorithm. Virologic outcome will be defined as the following categories:

- **HIV-1 RNA < 50 copies/mL:** this includes subjects who have the last available on-treatment HIV-1 RNA < 50 copies/mL in the Week 48 analysis window

- **HIV-1 RNA \geq 50 copies/mL:** this includes subjects
 - a) Who have the last available on-treatment HIV-1 RNA \geq 50 copies/mL in the Week 48 analysis window, or
 - b) Who do not have on-treatment HIV-1 RNA data in the Week 48 analysis window and
 - i) Who discontinue study drug prior to or in the Week 48 analysis window due to lack of efficacy, or
 - ii) Who discontinue study drug prior to or in the Week 48 analysis window due to reasons other than adverse event (AE), death, or lack of efficacy and have the last available on-treatment HIV-1 RNA \geq 50 copies/mL
- **No Virologic Data in the Week 48 analysis window:** this includes subjects who do not have on-treatment HIV-1 RNA data in the Week 48 analysis window because of the following:
 - a) Discontinuation of study drug prior to or in the Week 48 analysis window due to AE or death (regardless of whether the last available on-treatment HIV-1 RNA $<$ 50 copies/mL or not) or,
 - b) Discontinuation of study drug prior to or in the Week 48 analysis window due to reasons other than AE, death, or lack of efficacy and the last available on-treatment HIV-1 RNA $<$ 50 copies/mL or,
 - c) Missing data during the window but on study drug.

8.5.1.2. Analysis of Primary Efficacy Endpoint

The null hypothesis is that the proportion of subjects achieving HIV-1 RNA $<$ 50 copies/mL (as defined by the US FDA-defined snapshot algorithm) at Week 48 in B/F/TAF is at least 12% lower than the response rate in DTG + F/TDF; the alternative hypothesis is that the response rate in B/F/TAF is less than 12% lower than that in DTG + F/TDF.

Non-inferiority will be assessed using the conventional confidence interval approach. The point estimate of treatment difference (B/F/TAF – DTG+F/TDF) and the associated 2-sided 95% confidence interval will be constructed using a normal approximation method based on stratified Mantel-Haenszel proportions, where stratification factor include baseline HIV-1 RNA (\leq 100,000 copies/mL vs. $>$ 100,000 copies/mL).

It will be concluded that B/F/TAF is non-inferior to DTG + F/TDF if the lower bound of the 2-sided 95% CI of the difference (B/F/TAF – DTG+F/TDF) in the response rate is greater than -12%.

If non-inferiority of B/F/TAF to DTG+F/TDF is established, the lower bound of the 95% CI will be compared to 0; if the lower bound of the 95% CI is greater than 0, then superiority of B/F/TAF to DTG+F/TDF will be established.

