- The change from baseline in CD4 cell count and CD4% at Weeks 48 and 96

The secondary anti-HBV efficacy endpoints are:

- The proportion of subjects with plasma HBV DNA < 29 IU/mL at Week 96
- The proportion of subjects with ALT normalization at Weeks 48 and 96
- The proportion of subjects with HBsAg loss at Weeks 48 and 96

Pharmacokinetics:

Trough PK blood sample will be obtained 20-28 hours following the last dose at Weeks 4, 12, and 36. Following an observed dose, one post-dose PK blood sample will be collected between 1 and 4 hours post-dose at Weeks 8 and 24.

The plasma concentrations of bicitgravir, tenofovir alafenamide, and/or metabolites may be summarized using descriptive statistics.

CCI [REDACTED]

[REDACTED]

Statistical Methods:

The primary efficacy analysis will consist of a non-inferiority test of FDC of B/F/TAF versus DTG + F/TDF, with respect to the proportion of subjects who achieve HIV-1 RNA < 50 copies/mL at Week 48 as defined by the US FDA-defined snapshot algorithm. It will be concluded that B/F/TAF is non-inferior to DTG + F/TDF if the lower bound of the 2-sided 95% confidence interval (CI) of the difference (B/F/TAF – DTG + F/TDF) in the response rate (HIV-1 RNA < 50 copies/mL as defined by the US FDA-defined snapshot algorithm) is greater than -12%; ie, a margin of 12% is applied to non-inferiority assessment. The 95% CI will be constructed using a normal approximation method based on stratified Mantel-Haenszel proportions, where stratification factor includes baseline HIV-1 RNA ($\leq 100,000$ copies/mL vs. $> 100,000$ copies/mL).

The co-primary efficacy analysis will consist of a non-inferiority test of FDC of B/F/TAF versus DTG + F/TDF, with respect to the proportion of subjects with plasma HBV DNA < 29 IU/mL at Week 48 by Missing = Failure approach. It will be analyzed in a similar manner as described for the primary efficacy endpoint, except that the stratification factors include HBeAg status (positive vs. negative) and baseline HBV DNA ($< 8 \log_{10}$ IU/mL vs. $\geq 8 \log_{10}$ IU/mL).

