5. INVESTIGATIONAL MEDICINAL PRODUCTS

5.1. Randomization, Blinding and Treatment Codes

Subjects will be assigned a screening number at the time of consent. **Randomization and Day 1 visits cannot occur until the Investigator has received the results of the screening genotype report and subject eligibility has been confirmed.**

Once eligibility has been confirmed and prior to or during the Day 1 visit, the Investigator or designee will randomize the subject using the Interactive Web Response System (IWRS). Once a subject number has been assigned to a subject, it will not be reassigned to any other subject. The subject number assignment and randomization may be performed up to 3 days prior to the in-clinic Day 1 visit provided that all screening procedures have been completed and subject eligibility has been confirmed.

Subjects will be randomized in a 1:1 ratio to Treatment Group 1 or Treatment Group 2.

Randomization will be stratified by HBeAg (positive vs. negative), HBV DNA ($< 8 \log_{10}$ IU/mL vs. $\geq 8 \log_{10}$ IU/mL), CD4+ cell count (< 50 cells/ μ L vs. ≥ 50 cells/ μ L) at screening.

The IWRS will assign study drug bottle numbers of blinded FDC of B/F/TAF + placebo to match DTG + placebo to match F/TDF FDC, or DTG + F/TDF FDC + placebo to match FDC of B/F/TAF at each study visit for each subject.

At the End of Blinded Treatment Visit the IWRS will assign open label FDC of B/F/TAF.

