8.5.2. Secondary Analyses

8.5.2.1. Secondary anti-HIV Efficacy Analysis

The proportion of subjects who achieve HIV-1 RNA < 50 copies/mL at Week 96 as defined by the US FDA-defined snapshot algorithm, will be analyzed using the same method as for the primary efficacy endpoint.

The changes from baseline in CD4 cell count and CD4% at Weeks 48 and 96 will be summarized by treatment using descriptive statistics. The differences in changes from baseline in CD4 cell count and CD4% between 2 treatment groups and the associated 95% confidence intervals will be constructed using ANOVA models, including treatment (B/F/TAF vs. DTG + F/TDF) and baseline HIV-1 RNA (\leq 100,000 copies/mL vs. > 100,000 copies/mL) as fixed effects in the model.

In addition, missing CD4 cell count will be imputed using Last Observation Carried Forward (LOCF) method and analyzed similarly.

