3.3. Strata and Covariates

Randomization was stratified by HBeAg (positive vs. negative), HBV DNA (< $8 \log_{10} IU/mL$ vs $\geq 8 \log_{10} IU/mL$), CD4+ cell count (< $50 \text{ cells/}\mu L$ vs $\geq 50 \text{ cells/}\mu L$) at screening.

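### The protocol's HIV comparisons stratify on baseline HIV-1 RNA alone and leave out the randomised CD4 stratum; the estimate stays valid but is slightly less precise than it could be

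*Protocol*

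**What the plan says.** Protocol 5.1 gives the allocation rule: "Randomization will be stratified by HBeAg (positive vs. negative), HBV DNA" (below 8 against 8 or more log10 IU/mL) and CD4 count (below 50 against 50 or more cells/µL), all at screening. SAP 3.3 repeats it ("Randomization was stratified by HBeAg (positive vs. negative), HBV DNA" and CD4) and names no analysis covariate.

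The efficacy comparisons in the protocol use these factors:

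- **HIV primary, Week 48 (8.5.1.2):** "based on stratified Mantel-Haenszel proportions, where stratification factor include baseline HIV-1 RNA", at 100,000 copies/mL. The synopsis agrees: "where stratification factor includes baseline HIV-1 RNA".
- **HIV, Week 96 (8.5.2.1):** "will be analyzed using the same method as for the primary efficacy endpoint".
- **CD4 and CD4% change (8.5.2.1):** "ANOVA models, including treatment (B/F/TAF vs. DTG + F/TDF) and baseline HIV-1 RNA".
- **HBV co-primary (8.5.1.3):** as for HIV, "except the stratification factors include HBeAg status (positive vs. negative) and baseline HBV DNA".
- **Secondary HBV endpoints (8.5.2.2):** HBeAg and baseline HBV DNA.

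The protocol gives no reason for the difference between the randomisation factors and the HIV strata. The supplied SAP covers the final analysis, plans no between-group comparison for the All B/F/TAF analysis, and states in 6.4 that the protocol's efficacy analysis is unchanged. For the Week 48 and Week 96 methods it refers to earlier SAPs (6.1.1, 6.2.1.2).

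**The concern.** The HBV comparisons carry the HBV-related randomisation factors into the analysis. The HIV comparisons carry none of the three, although CD4 is the factor most directly tied to HIV disease. When allocation is balanced on a prognostic factor, the true spread of the treatment difference shrinks. An analysis that ignores the factor does not credit that gain, so it reports a standard error larger than it needs to be.

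This matters somewhat more than usual because the HIV test is the gate. Under 8.5.1.3, if HIV non-inferiority fails, the HBV co-primary is not tested. Planned HIV power is 90% at exactly 120 per arm, so there is little reserve.

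**Working it through.** **1. Factors side by side**

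| Factor | Randomisation | HIV Wk 48 and Wk 96 | CD4 change | HBV endpoints |
|---|---|---|---|---|
| HBeAg | yes | no | no | yes |
| HBV DNA | yes | no | no | yes |
| CD4 < 50 | yes | no | no | no |
| HIV-1 RNA | no | yes | yes | no |

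The CD4 row has no entry under any comparison.

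**2. The plan's own power (Protocol 8.8)**

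Inputs: 120 per arm, margin 0.12, one-sided 0.025, equal response in both arms. Power = Φ(0.12/SE − 1.960), with SE = √(2p(1−p)/120).

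- HIV, p = 0.91: SE = √0.001365 = 0.03695; 0.12/0.03695 = 3.248; Φ(1.288) = 0.901. Stated: 90%.
- HBV, p = 0.88: SE = √0.00176 = 0.04195; 0.12/0.04195 = 2.860; Φ(0.900) = 0.816. Stated: 81%.

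Both reproduce without any strata, so the sample size does not depend on this choice.

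**3. What CD4 could add, in closed form**

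The documents give neither the share w of subjects below 50 cells/µL nor their response, so both are assumptions. With overall response 0.91 and a gap d between the two CD4 strata, the share of variance explained is r = w(1−w)d²/(0.91 × 0.09). Because allocation is balanced on CD4, the true SD of the difference is already 0.03695·√(1−r), whether or not CD4 is in the analysis. Only the reported SE differs:

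- without CD4: power = Φ[(0.12 − 1.960 × 0.03695)/SD]
- with CD4: power = Φ[0.12/SD − 1.960]

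| w | response, CD4 < 50 | response, rest | d | r | SD | power without | power with | gain, points |
|---|---|---|---|---|---|---|---|---|
| 5% | 80% | 91.58% | 0.1158 | 0.008 | 0.0368 | 90.2% | 90.3% | 0.1 |
| 20% | 80% | 93.75% | 0.1375 | 0.037 | 0.0363 | 90.5% | 91.1% | 0.6 |
| 20% | 78% | 94.25% | 0.1625 | 0.052 | 0.0360 | 90.7% | 91.5% | 0.8 |

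This is CD4's effect on its own, before HIV-1 RNA is taken into account.

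**4. Simulation of the actual choice, HIV-1 RNA against HIV-1 RNA × CD4**

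6,000 trials per row, N = 240, allocation balanced within CD4. Assumed: 40% above 100,000 copies/mL with response 4 points lower. Mantel-Haenszel difference with plug-in variance. Type I error is one-sided at a true difference of −12 points (Monte Carlo error about 0.002).

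| w, response | SE, RNA | SE, RNA × CD4 | power, RNA | power, RNA × CD4 | type I, RNA | type I, RNA × CD4 |
|---|---|---|---|---|---|---|
| 5%, 80% | 0.0364 | 0.0357 | 90.2% | 90.7% | 0.028 | 0.031 |
| 10%, 80% | 0.0364 | 0.0354 | 90.8% | 91.5% | 0.031 | 0.032 |
| 15%, 75% | 0.0364 | 0.0347 | 91.1% | 92.4% | 0.025 | 0.030 |
| 20%, 80% | 0.0365 | 0.0352 | 90.4% | 91.6% | 0.026 | 0.030 |

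The gain is 0.5 to 1.3 points, and 0.5 to 1.2 in the rows with 80% response.

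**5. How much of that gain is real**

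Type I error rises in every row. At w = 5% the low-CD4 stratum holds 0.05 × 240 = 12 subjects, about 3 per arm in each HIV-1 RNA cell, and the plug-in variance is too small in cells of that size. A separate simulation of the four-cell analysis gave plug-in gains of about 0.8–1.2 points, with one-sided error 0.026–0.031 against 0.022–0.027 for HIV-1 RNA only. Replacing the plug-in variance with Sato's or an n−1 version largely removed the excess and left a gain of about 0.1–0.7 points, in line with step 3.

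**The case against.** The strongest reply is that nothing here is invalid. Adjusting for a pre-specified baseline covariate that was not a randomisation factor is legitimate. Leaving out a balanced prognostic factor keeps the difference unbiased on average and the interval a little wide, which is conservative for non-inferiority. That stands.

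A reader might infer that dropouts leave a CD4 imbalance in the primary result. The documents give little support for this. Under the snapshot algorithm (8.5.1.1), subjects who discontinue or have missing data stay in the denominator as non-successes. The full analysis set (8.2.1.2.1) drops only undosed subjects and those with no on-drug post-baseline HIV-1 RNA or HBV DNA result.

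A reader might also infer a large loss. The variance formula reaches about 9% (roughly 24 of 240 subjects) only with 25% of subjects below 50 cells/µL and a 20-point deficit. No document gives either figure. For context only, since they were not coinfection trials, the two studies behind the 91% had 11% and 12% below 200 cells/µL (Protocol 1.2.3.4).

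Finally, the obvious remedy has its own cost: crossing CD4 with HIV-1 RNA and keeping the plug-in variance raises type I error slightly. That also stands and shapes the fix.

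**Conclusion.** The point holds as a small loss of precision, not as an error in the estimate. In the protocol, the Week 48 and Week 96 HIV comparisons stratify only on a factor that was not randomised on, and no efficacy comparison uses the randomised CD4 stratum. It would go too far to say that no planned analysis anywhere uses CD4: the Week 48 and Week 96 SAPs were not available, and they may have added it.

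The size rests on assumed figures: 5–20% of subjects below 50 cells/µL, 78–80% response among them, 91% overall. On those figures power rises by up to about 1 point with the plug-in variance, and by about 0.1–0.7 points with a variance suited to small cells. If low CD4 is rare or not prognostic, the gain is close to nil. The case for the change is that it costs very little and acts on the test that gates the HBV co-primary.

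**What to change.** Define the Mantel-Haenszel strata for the Week 48 and Week 96 HIV analyses as randomised CD4 stratum (below 50 against 50 or more) crossed with baseline HIV-1 RNA (at most 100,000 against above), in 8.5.1.2, 8.5.2.1 and the synopsis. Add two safeguards:

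- Pool over HIV-1 RNA within a CD4 stratum whenever a cell is sparse, not only when an arm is empty, with the threshold written down beforehand.
- Use a variance estimator that is valid in sparse strata, such as Sato's.

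SAP section 6 says the Week 48 and Week 96 analyses have been completed. Redefining the primary strata now would be post hoc, so for this trial report the result as a labelled sensitivity analysis beside the planned one. If the earlier SAPs already include CD4, a cross-reference is enough.

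The cost is a few lines of text and one extra table; the CD4 strata are already in the randomisation system. The remaining downside is a small risk of sparse cells, and a slight rise in type I error if the plug-in variance is kept.
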